Transcranial magnetic stimulation (TMS): Motor evoked potentials (MEPs) in the tibialis anterior and rectus femoris muscles will be evoked by TMS of the contralateral motor cortical leg area using a Magstim 200² stimulator (Magstim, UK) through a double cone coil and a monophasic current waveform delivered at 4-s intervals. The motor threshold for both muscles will be identified⁶⁵ and that intensity will be used to elicit and average twenty MEPs at each timepoint²⁴. Average MEP response amplitude will be used to quantify changes in corticospinal tract excitability¹⁵. If no motor threshold is detected at 100% device stimulation intensity due to SCI (and interrupted circuits), the 100% stimulation intensity or the maximum tolerable intensity will be used. MEP responses will be measured during rest and during an active contraction (Motor Tasks, see below) before and after BoMI training, as well as with and without SCS. To estimate changes in MEPs, response amplitudes under different conditions will be normalized to the baseline (before training, resting) response.

Motor tasks: Immediately before after the BoMI session, participants will wear a VR headset (Oculus Quest 2, Facebook, CA) to block their view. The IMUs on the legs will measure and digitize their leg joint angles. A real-time virtual representation of one of their joint angles will be presented through the VR. Participants will be asked to perform two tasks requiring different types of motor control. In the range-of-motion task, participants will be instructed to flex or extend their legs to surpass a virtual target of a specified amplitude. In the precision-control task, participants will have to move their joint and hold the position within a target range of a specified amplitude for 1 second. We will examine motor-evoked potentials elicited by TMS (*Aim 1*) and the StartReact response (*Aim 2*) as individuals perform the task under two conditions: with SCS and without SCS using the knee and ankle joints. As an alternative to the VR headset, a wall projector will be used to perform the motor tasks.

BoMI Training: Participants will perform visuo-spatial motor tasks over a 45min session with SCS. The tasks will consist of different types of game-like activities like center-out reaching, pong, solitaire, Tetris, and other flash games.

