Support of limb weight may introduce a force production confound when participants have to generate torque to move their foot compared to their whole leg. If this is the case, we will perform the motor task evaluations as participants lay on their side as manual support is provided to counter the effects of gravity.

7.2 Aim 2: Determine which kinds of SCS-enabled movements are mediated by the reticulospinal tract

Using the same protocol as Aim 1, we will test whether SCS can enhance the StartReact response time and amplitude. To quantify changes in neural excitability of the reticulospinal tract, we will compare the StartReact response⁷⁰ (a shortening in response time after a startling auditory stimulus) as participants perform the motor tasks before and after BoMI training.

StartReact response: Participants will be instructed to reach the target as fast as possible after it is presented. Response time will be identified from EMG activity⁷¹ and measured when the target is presented alone (visual reaction time), when it is paired with a soft auditory stimulus (80 dB, 500 Hz, 50 ms, visual-auditory reaction time), or with a startling acoustic stimulus (120 dB, 500Hz, 50ms, visual-startle react time) presented through audio speakers (T-15, Polk Audio). To quantify changes in StartReact responses, response times under different conditions will be normalized to the baseline response.

Expected outcomes: Based on previous studies by other groups^{47,71,72}, I expect the StartReact response time to be the shortest for the startle response, where the reticulospinal tract is engaged. Furthermore, I expect that SCS will have an additional enhancement of this response, but only for tasks that require a high involvement from the reticulospinal tract. *We hypothesize that SCS will enhance the StartReact response for the range-of-motion task in proximal muscles (rectus femoris), but not for precision-control movements, or movements with distal muscles (tibialis anterior).*

8. Data Analysis and Statistical Plan

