Average MEP and StartReact responses (of 20 responses) will be used to quantify changes in corticospinal and reticulospinal tract excitability¹⁵. A paired sample t-test of response amplitude and latency (time from stimulation to muscle response) will be used to test the hypothesis that BoMI training with SCS results in enhanced corticospinal tract excitability during precision-control movements and reticulospinal tract excitability during range-of-motion movements. In addition, a Student's *t*-test with a Holm-Sidak adjustment for multiple comparisons will be performed to compare the difference between changes in corticospinal excitability induced by the type of motor task (precision control vs. range-of-motion), joint (ankle vs. hip), and group (control vs. SCI).

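### Active-task MEPs are analysed with no check on contraction level at the pulse, so a shift in contraction with training or SCS could be read as a change in corticospinal excitability

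*Combined protocol and SAP*

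**What the plan says.** Section 7.1 (Aim 1), under Transcranial magnetic stimulation, names the outcome: "Average MEP response amplitude will be used to quantify changes in corticospinal tract excitability". Section 8 repeats this for averages of 20 responses. The same Aim 1 paragraph states that "MEP responses will be measured during rest and during an active contraction", before and after BoMI training and with and without SCS, and that "response amplitudes under different conditions will be normalized to the baseline (before training, resting) response".

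Under Motor tasks, the instruction for range of motion is that "participants will be instructed to flex or extend their legs to surpass a virtual target of a specified amplitude". For precision control, they must "move their joint and hold the position within a target range of a specified amplitude for 1 second". MEPs are examined "as individuals perform the task under two conditions: with SCS and without SCS using the knee and ankle joints". (The Aim 1 introduction and section 8 name hip and ankle instead; that is a separate matter.)

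Section 8 plans a paired t-test of amplitude and latency for the effect of BoMI training with SCS. It adds Student's t-tests with a Holm-Sidak adjustment, comparing changes in excitability by task, joint and group. Neither test has a covariate.

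The Aim 1 text ends by acknowledging that "Support of limb weight may introduce a force production confound" when moving the foot is compared with moving the whole leg. If that happens, participants are to be tested lying on their side with manual support against gravity.

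**The concern.** An active MEP reflects both the state of the descending pathway and how strongly the target muscle is contracting when the pulse arrives. The plan accepts the principle, since it separates rest from active contraction and worries about force production. Yet it neither sets, measures nor adjusts for contraction level in the MEP analysis. Dividing by a resting MEP does not help, because the resting value carries no information about contraction during the task.

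There are grounds in the text for expecting contraction to move. The Aim 1 introduction describes SCS as raising the functional state of spinal networks and says epidural SCS can enable force production in paralysed muscles. Section 9.4 allows SCS amplitude to be set where a motor response appears. TMS pulses come every 4 seconds, with no stated timing relative to the phase of movement or hold.

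Aim 1 hypothesises a specific pattern: SCS enhances MEPs in precision, distal movements and not in range-of-motion or proximal ones. If training or SCS shifts contraction more in some conditions than in others, that pattern could be produced or masked with no change in corticospinal excitability.

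**Working it through.** The documents give no alpha, effect size, MEP variance or background EMG level, so there is no plan figure to reproduce. The check has four parts.

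**1. Is contraction controlled anywhere?**
- Both task targets are joint positions (section 7.1, Motor tasks). No EMG or force level is set.
- The EMG paragraph in section 7 defines a rectified moving average in a centred 250 ms window. Centred on the pulse, it would reach 125 ms either side and so include the MEP itself.
- No pre-stimulus window, matched contraction level, trial-rejection rule or covariate is given.
- The posture step is conditional, has no criterion for being triggered, and covers limb weight only. It does not reach SCS on/off, precision versus range-of-motion, or a change in effort over training.

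**2. What does a stable contraction difference do?** Suppose the active-to-rest ratio before training is 3 in one task and 2 in the other (illustrative values), purely because contraction differs.
- No true change: 3 − 3 = 0 and 2 − 2 = 0. The contrast of changes is 0.
- The same true rise of 10% in both: 3 × 1.10 − 3 = 0.3 and 2 × 1.10 − 2 = 0.2. The contrast is 0.1, an apparent task effect.
- Relative to each task's own pre-training value: 3.3/3 = 1.10 and 2.2/2 = 1.10. The contrast is 0.

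**3. What does a shift in contraction do?** Assume the within-person change in log MEP is b × log(background EMG ratio) + noise, with no true change in excitability. Test it with a two-sided 0.05 paired t-test, using n = 12 (SCI) and n = 16 (unimpaired per protocol type). For a ratio of 1.2, the bias in log MEP is 0.5 × ln 1.2 = 0.09 to 1 × ln 1.2 = 0.18. With the ratio the same in every participant, b from 0.5 to 1 and noise SD from 0.3 to 0.5 (all assumed), the noncentral t distribution gives these false-positive rates:

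| Background EMG ratio | n = 12 | n = 16 |
|---|---|---|
| 1.0 | 5% | 5% |
| 1.1 | 6–17% | 7–22% |
| 1.2 | 9–48% | 11–62% |
| 1.5 | 25–99% | 33–100% |

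A simulation (20,000 runs) let the log background change vary between participants with SD 0.25, taking b = 1 and noise SD 0.3. At a ratio of 1.2 the unadjusted rates were 32% (n = 12) and 42% (n = 16). Adjusting for the change in log pre-stimulus EMG gave 4.8% and 5.3%. That recovery is partly built in: the model is correct and EMG is measured without error.

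**4. Can the covariate be measured cleanly?** The SCS paragraph gives 1–100 Hz. A 100 ms window therefore holds on average 0.1 s × 100 Hz = 10 SCS pulses at the top of the range, 0.1 × 10 = 1 at 10 Hz, and 0.1 × 1 = 0.1 at the bottom. These occur only when SCS is on, so uncleaned windows would not measure the same thing in the two SCS states.

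**The case against.** Four objections have force.

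*Section 8 tests changes.* A reader might infer that any difference in contraction between tasks or joints would be reported as a corticospinal effect. The documents do not support that. On its natural reading, section 8 tests a change over training and differences between changes, and part 2 of the working shows that a stable difference yields nothing when nothing truly changes. This stands and narrows the point to shifts with training or SCS, plus the rescaling. SCS on/off belongs to the design and the hypothesis, but section 8 names no on/off test.

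*Some data are less exposed.* Resting MEPs are collected before and after training and with and without SCS. They do not answer the task hypotheses, but they are a useful comparison. EMG envelopes are also produced for quantification, so it would be wrong to say the EMG goes unused; what is missing is a stated use in the MEP analysis.

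*Adjustment can mislead.* SCS artefact and SCS-evoked responses can contaminate the pre-stimulus window in one state only. ASIA A participants are eligible, and some may have background EMG near noise. Both stand and limit the adjusted analysis.

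*Background EMG may carry the effect.* In a voluntary task it partly reflects descending drive. It is tempting to conclude that an effect which vanishes on adjustment is not corticospinal; that does not follow.

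**Conclusion.** The gap is real. Nothing in the plan shows whether contraction at the pulse was the same before and after training or with and without SCS, and dividing by a resting MEP cannot show it. If contraction shifts, a change in active MEP amplitude cannot be attributed to the corticospinal tract. If contraction merely differs between tasks or joints and stays put, it creates no false change, but it can make equal proportional changes look like a task effect.

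The size of the bias cannot be derived from the documents. The false-positive rates above depend on an assumed slope, noise level and background shift. They show what would follow if contraction shifted, not that it will. A reader might also turn an assumed gap in background EMG between tasks into a percentage bias in the Aim 1 result. That would be a difference in level, which is not the bias in a change score. The point concerns MEP amplitude and leaves the latency test aside.

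**What to change.** Add the following to section 8.

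- For each TMS pulse, compute mean rectified EMG of the target muscle in a fixed pre-stimulus window, with SCS artefact and SCS-evoked responses blanked. Report it by task, joint, SCS state, before/after and group.
- Keep the planned unadjusted tests. Beside them, report a sensitivity analysis of log MEP amplitude adjusted for log pre-stimulus EMG, or restricted to trials matched on it. Use it primarily for before/after and task contrasts within the same SCS state.
- Interpret an adjusted SCS on/off contrast only where the cleaned windows are comparable. Flag participants whose background EMG is at noise level.
- Express each active-task change relative to that task's own pre-training value, and show the resting MEP contrasts next to it.
- If an effect disappears on adjustment, state that it cannot be separated from a change in contraction level.

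The cost is a little more analysis work, including artefact blanking, on EMG from the muscles already recorded; no extra visits or participants are needed. The drawback is that adjustment may remove part of a real effect acting through background activity, which is why both estimates are shown.

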To better understand SCS-mediated neurorecovery, studies in rodent models of SCI using viral tracing¹³ and optogenetics¹⁴ suggest that corticospinal and reticulospinal projections mediate the voluntary control of paralyzed areas enabled by SCS, and activity-dependent reorganization of these circuits may be a primary contribution towards the restoration of function that has been observed in humans⁷⁻⁹. While direct recordings of these neural structures through viral tracing and optogenetics are not currently possible in humans, experimental paradigms exist to evaluate their involvement and contribution during SCS and motor tasks^{11,15}. Twenty minutes of SCS during rest has an excitatory effect at subcortical, but not cortical levels¹¹. However, it remains unclear whether this excitatory effect can be further enhanced by combining SCS with active voluntary movement. Indeed, despite the motor-enabling effects of SCS having been first observed half a century ago¹⁶, a major breakthrough in SCI research came from the combination of SCS with activity-based training^{4,5,7-9,17}. Moreover, while SCS can immediately enable a broad range of behaviors in animal models of paralysis^{13,18-20}, independent stepping without stimulation in humans has only been observed after more than a year of intense rehabilitation with SCS^{8,9,21}. In this work, we will evaluate corticospinal and reticulospinal tract excitability via transcranial magnetic stimulation (TMS) and reaction to a loud auditory stimuli (StartReact) respectively. Having a clear understanding of the neural mechanisms that are enhanced by SCS can allow the development of therapies that directly target the excitability and plasticity states of these structures towards improved and accelerated recovery.

3. Background and Significance

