3.1 Rationale for this study

This 1-year study will provide the necessary data to prepare a clinical trial investigating whether activity-dependent reorganization of cortico- and reticulospinal circuits are primary contributors towards the long-lasting improvements in function that have been observed in humans. Moreover, we will study whether different types of training used in rehabilitation can be used to enhance the excitability of these neural structures and evaluate their role in the learning of skilled motor tasks²²⁻²⁵. An understanding of how we can accelerate plasticity through residual cortical and reticulospinal connections may enable the development of rehabilitation strategies that take advantage of patient-specific residual functions to further augment recovery.

4. Study Objectives

The goal of this project is to generate evidence-based knowledge of changes in the short-term excitability of corticospinal and reticulospinal neural structures that may mediate immediate improvements in motor function enabled by SCS.

Aim 1. Determine which kinds of SCS-facilitated movements are mediated by the corticospinal tract. I will use TMS to test whether SCS can enhance motor evoked potential (MEP) response time and amplitude as individuals use their legs to perform motor control tasks with different levels of dexterity.

Aim 2. Determine which kinds of SCS-facilitated movements are mediated by the reticulospinal tract. Using the same protocol, I will test whether SCS can enhance StartReact response time and amplitude.

5. Selection of Subjects – Inclusion/Exclusion Criteria

We plan to include in this study a total of 100 unimpaired and 12 SCI human volunteers over the course of one year.

Data collection will be performed at Washington University in St. Louis Danforth and Medical campus. Subjects will be referred by Drs. [name], [name], [name], [name], and [name], who are co-investigators on this project.

Approximately equal numbers of men and women will be recruited from all ethnic and racial groups. The racial composition of the population in St. Louis is approximately 44% Caucasian, 46% Black or African American, 4% Asian, 4% Hispanic, 2% Other. This will be the expected composition of our volunteer pool, of which the minority portion exceeds the national norm.

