7.1 Procedure Schedules – Full Protocol

SCI and Controls – Complete protocol

PROCEDURE	7.2 INITIAL EVALUATION			7.3 AIM 1	7.4 AIM 2
	Visit #1 Functional Mapping	Visit #2 Range of Motion	Visit #3 Familiarization	Visit #4 TMS	Visit #5 StartReact
Kinematic recordings					
EMG recordings					
Transcutaneous SCS					
BoMI					
Motor tasks					
TMS					
StartReact					

7.2 Initial evaluation: Determine the effect of SCS on motor responses and range of motion

To determine an initial baseline for each participant, we will evaluate motor responses elicited by transcutaneous SCS in the initial evaluation phase. Participants will visit the lab for 1) a functional mapping where we measure spinal responses elicited by SCS, 2) a range of motion evaluation where we measure the range of motion on different joints with and without SCS, and 3) a familiarization phase where participants learn to control the body-machine interface using their leg movements supported by SCS.

Participants: 100 unimpaired participants and 12 participants with spinal cord injury (spinal cord injury level C4-T9) with motor impairments in the legs (complete ASIA A, or incomplete ASIA B, C, or D) and in the chronic stage of SCI (>6 months postinjury) will participate in this experiment, which will be submitted for review and approval to Washington University School of Medicine Institutional Review Board. Unimpaired participants will be recruited to perform either one of the five potential visits (Visits# 1-5) or all five visits. Approximately 16 unimpaired participants are expected to complete each type of protocol. SCI participants will be recruited for the five visits in total.

Experiments with unimpaired, control participants will be used to refine collection procedures and instruments and to prepare an improved, more refined research design that will ensure effective and high-quality data collection with SCI participants. Data collected on control subjects will also be used to establish baseline behavior for comparison of SCI participant task performance and may be used to generate generalizable knowledge.

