An increasing number of studies supports the view that SCS can restore posture, stepping, and voluntary walking in humans with SCI^{4,7,17}. The prevailing view is that by elevating the functional state of spared spinal sensory-motor networks below the lesion, residual descending pathways can transmit activity that enables and amplifies voluntary motor control¹⁵. Although epidural SCS can enable force production in paralyzed muscles⁷, whether motor improvements are mediated by the corticospinal tract or the reticulospinal remains unknown.

In a 45-min session, we will deliver non-invasive transcutaneous SCS to the lumbosacral enlargement as participants use their SCS-facilitated leg movements to control a non-invasive body-machine interface (BoMI) on a computer screen and perform game-like activities^{62,63}. To determine which kinds of SCS-enabled movements are mediated by corticospinal networks, participants will perform two motor tasks before and after training requiring different degrees of dexterity: precision control vs. maximum range of motion; using two types of movements: hip vs. ankle flexion. To quantify changes in neural excitability of the corticospinal tract, we will compare motor-evoked potentials (MEPs) elicited by transcranial magnetic stimulation of the leg motor cortex⁶⁴ as participants perform the motor tasks. We postulate that MEP responses will be enhanced for the precision-control task in distal muscles (tibialis anterior), which are thought to require a high involvement from the corticospinal tract. *Our hypothesis is that SCS will further enhance the MEP response for these movements, but not for range-of-motion movements, or movements with proximal muscles (rectus femoris).*

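### Section 8 names no stimulation-on versus stimulation-off contrast for either aim, and gives Aim 2's task and muscle selectivity hypothesis no direct test

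*Combined protocol and SAP*

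**What the plan says.** **The question.** Section 4 sets the goal as short-term excitability changes that "may mediate immediate improvements in motor function enabled by SCS". Aim 1 is to "test whether SCS can enhance motor evoked potential (MEP) response time and amplitude" across tasks of differing dexterity. Aim 2 says "I will test whether SCS can enhance StartReact response time and amplitude" under the same protocol. The Aim 1 hypothesis in Section 7 concerns precision control with the tibialis anterior: "SCS will further enhance the MEP response for these movements, but not for range-of-motion movements", nor for the rectus femoris. The Aim 2 hypothesis is the mirror image: enhancement of StartReact for range of motion with the rectus femoris, but not for precision control or the tibialis anterior.

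**The data.** In the Aim 1 methods, MEPs are measured at rest and during contraction, before and after BoMI training, and with and without SCS. The motor-task paragraph there plans both MEP and StartReact with and without SCS. BoMI training is a 45-minute session delivered with SCS, and no training without SCS is described.

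**The analysis.** Section 8 gives two analyses. A paired t-test of amplitude and latency "will be used to test the hypothesis that BoMI training with SCS results in enhanced corticospinal tract excitability during precision-control movements", and likewise reticulospinal excitability in range-of-motion movements. A Student's t-test with Holm-Sidak adjustment then compares changes in corticospinal excitability by task, joint and group.

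**The concern.** The stated analysis does not answer the stated question. The hypotheses are about SCS, while the paired test is about training combined with SCS. If the pair is before versus after training, a positive result could come from SCS, practice, fatigue or elapsed time. If the pair is SCS on versus off, the plan does not say so and does not say at which timepoint. The timepoint matters, because a post-training off measurement follows 45 minutes of stimulation. With the pair left open, it could be chosen once results are known.

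For Aim 2, a claim of the form that SCS helps here but not there needs a test of the difference between the two effects. Section 8 offers only a test within range-of-motion movements, with no muscle named. Attributing effects to a tract and a type of movement is the purpose of the study, and Section 3.1 says the results will be used to prepare a clinical trial.

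**Working it through.** The documents give no figure to reproduce on this point. The main check compares the text.

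| Needed by the hypotheses | Recorded (Section 7) | Tested (Section 8) |
|---|---|---|
| MEP, SCS on vs off | Yes | Not named |
| StartReact, SCS on vs off | Yes | Not named |
| MEP: SCS effect compared between tasks and joints | Yes | Task and joint are compared, but on a change whose pair is undefined |
| StartReact: SCS effect compared between tasks and joints | Yes | Absent |

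SCS condition is a factor in neither analysis. Three comparison factors are named for corticospinal excitability and none for reticulospinal excitability.

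**Illustrations.** The documents give no effect size, SD or alpha, so these inputs are assumed. Tests are paired, two-sided at 0.05. Effects are in SDs of the paired difference. n = 12 is the planned SCI group (Section 8.4). Power is the noncentral t probability beyond ±2.201 (11 df), with noncentrality δ√12.

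*(a) Selectivity inferred from significance.* Let SCS act equally in both tasks, and let r be the correlation between the two on-minus-off differences. At r = 0 the chance of a significant result in the expected task and not in the other is p(1 − p), where p is the power:

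- 0.3 SD: 0.158 × 0.842 = 0.133
- 0.5 SD: 0.353 × 0.647 = 0.228
- 0.8 SD: 0.714 × 0.286 = 0.204

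At r = 0.5, simulation (100,000 runs) gives 0.099, 0.161 and 0.146. The range is therefore about 10% to 23%. A direct test of the difference rejects in about 5% throughout. At n = 16 ("Approximately 16 unimpaired participants are expected to complete each type of protocol") the range is about 10% to 25%. These figures depend on the inputs: at n = 12 they fall to 2.7% to 3.4% for 1.2 SD (r 0 to 0.5), and to 6.6% to 10.3% for 0.3 to 0.8 SD at r = 0.8.

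*(b) Before/after read as an SCS effect.* A pure practice shift of 0.2, 0.3 or 0.5 SD, with no SCS effect, would be significant in 10%, 16% or 35% of trials at n = 12. This applies only if the before/after result were put to that use.

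*(c) Power of a direct SCS-by-task test.* Take 0.8 SD in one task and none in the other. The standardised difference is 0.8/√(2(1 − r)), which is 0.566 at r = 0 and 0.8 at r = 0.5. The Sidak level for k tests is 1 − 0.95^(1/k), the strictest Holm-Sidak step. Two interactions for two outcomes make 4 tests; analysing amplitude and latency for each makes 8.

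| Tests | Level | Power, r = 0 | Power, r = 0.5 |
|---|---|---|---|
| 1 | 0.0500 | 43% | 71% |
| 4 | 0.0127 | 21% | 46% |
| 8 | 0.0064 | 14% | 34% |

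**The case against.** Four arguments have weight.

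- **Training with SCS is a legitimate question.** The Introduction reports that "Twenty minutes of SCS during rest has an excitatory effect at subcortical, but not cortical levels" and adds that "it remains unclear whether this excitatory effect can be further enhanced by combining SCS with active voluntary movement". A before/after comparison of combined training answers that question. This stands: the test should stay, but it does not answer the SCS hypotheses.
- **The intent is visible.** Aim 2 follows the same protocol as Aim 1, on/off recording is planned for both, and limiting the factor comparisons to corticospinal excitability may be a drafting slip. That makes the gap one of wording, but it does not supply the missing test.
- **The lead timepoint is partly the sponsor's choice.** Section 7 frames measurement as before and after training. Naming a timepoint in advance is the requirement; which one leads is a recommendation.
- **The error rates depend on the chosen inputs.** They do. The principle that a significant result beside a non-significant one does not show a difference needs no numbers.

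A reader might infer that the study cannot answer its question or lacks the data. The documents do not support that, because with- and without-SCS recordings are planned for both outcomes. A reader might also infer that Section 8 commits to a before/after pair. That is the natural reading of its wording and of the Aim 2 methods, but it remains an inference.

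**Conclusion.** The point holds on the text. Section 8 specifies no SCS-on versus SCS-off contrast for either aim, its paired test has an undefined pair, and Aim 2's selectivity hypothesis has no direct test. These conclusions need no outside figure. The percentages are illustrations under assumed effect sizes, correlations and a two-sided 0.05 level, and should not be read as this trial's error rates.

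The severity is should-fix. The stated analysis does not answer the stated hypotheses, but this is a small mechanistic study with the necessary recordings already planned, and nothing in the documents shows that the contrast would in fact be chosen after seeing data.

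**What to change.** In Section 8:

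1. For each aim, prespecify the within-participant SCS-on minus SCS-off difference as the test of the SCS hypothesis, and name its timepoint. Before training is suggested: it fits the Section 4 goal of immediate improvement and avoids carry-over from the 45-minute SCS session. Report the other timepoint separately.
2. Test SCS by task and SCS by joint or muscle directly, for StartReact as well as MEP, with estimates and intervals. State whether the Holm-Sidak adjustment covers these tests.
3. State which StartReact measure enters the contrast (visual, visual-auditory or visual-startle time, or a difference between them) and which normalisation baseline applies. The Aim 1 methods use the resting response before training; the Aim 2 methods refer only to a baseline response.
4. Keep the before/after test for the training-with-SCS hypothesis, define its pair, and do not read it as an effect of SCS alone.
5. Balance or record the order of on and off measurements, which the documents do not give.

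The cost is mostly plan wording, plus attention to measurement order. The real downside is low power for the selectivity tests: 43% to 71% unadjusted under the assumptions above, falling to 21% to 46% over 4 tests or 14% to 34% over 8. Intervals should therefore carry the interpretation, and a non-significant interaction should not be read as absence of selectivity. Section 7 is inconsistent on whether the proximal joint is hip or knee; that is a separate point and adds nothing to the severity here.
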